#### 2.1.6 Treatment groups for analysis

Summaries will be presented according to the following combined treatment groups. If not mentioned otherwise, data from subjects discontinuing from the investigational product in studies D3461C00004 or D3461C00005, or who elect not to participate in the LTE, will be considered up to the adjusted analysis-defined visit window of Week 52 (ie, up to Day 378).

Primary:

- **Randomised Anifrolumab 300 mg:** Subjects randomised to anifrolumab 300 mg in studies D3461C00004 or D3461C00005 using all data from start of feeder study to end of LTE.
- **Randomised Placebo:** Subjects randomised to placebo in studies D3461C00004 or D3461C00005 using data from start of feeder study up until switch to anifrolumab 300 mg or to end of LTE for subjects re-randomised to placebo in LTE, respectively.

Supportive:

- **Placebo Feeder + Placebo LTE:** Subjects randomised to placebo in Studies D3461C00004 or D3461C00005 and re-randomised to placebo in LTE using all data from start of feeder study to end of LTE. Data from subjects not randomised into the LTE for any reason but that would have been re-randomised to placebo are included in this treatment group up to Week 52. Subjects who are not randomised into the LTE study will be assigned to Placebo or anifrolumab 300 mg via a

separate randomization process in order to determine who would have been re-randomised to placebo.

- **All Anifrolumab:** Subjects randomised to anifrolumab in studies D3461C00004 or D3461C00005, regardless of dose, and subjects randomised to placebo in studies D3461C00004 or D3461C00005 and then re-randomised to anifrolumab 300 mg in LTE, using all data from start of feeder study or switch to anifrolumab, respectively, to end of LTE. Baseline data from the feeder study will be included for all subjects.

Additional supportive:

- **Placebo Feeder + Anifrolumab 300 mg LTE:** Subjects randomised to placebo in studies D3461C00004 or D3461C00005 and then re-randomised to anifrolumab 300 mg in LTE using data from start of feeder study to end of LTE. Data from subjects not randomised into the LTE for any reason, but that would have been re-randomised to anifrolumab 300 mg are included in this treatment group up to Week 52. Subjects who are not randomised into the LTE study will be assigned to Placebo or anifrolumab 300 mg via a separate randomization process in order to determine who would have been re-randomised to anifrolumab 300 mg.

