### 3. PRIMARY AND SECONDARY VARIABLES

If not stated otherwise, not only data collected during the LTE study but also data collected in the Phase 3 feeder Studies D3461C00004 and D3461C00005 will be considered. If not stated otherwise, all references to Day 1 and date of first dose of investigational product, respectively, refer to the respective day in the Phase 3 feeder studies. The date of last dose of investigational product refers to the last dose during the LTE study for subjects who started the LTE study and to the last dose in the Phase 3 feeder studies for subjects not continuing in the LTE study.

Baseline is defined as baseline of the Phase 3 feeder studies, i.e., the last non-missing measurement prior to dose administration on Day 1. If the Day 1 value is missing or is invalid or is collected after administration of investigational product, the latest assessment prior to dose administration on Day 1 will serve as baseline.

[REDACTED]

[REDACTED]

If not stated otherwise, change from baseline will be calculated as value at the respective post-baseline time point minus value at baseline.

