### 3.1.1 Adverse events

Adverse events experienced by the subjects will be collected throughout the entire studies and will be coded using the latest version of Medical Dictionary for Regulatory Activities (MedDRA).

Adverse event data will be categorised according to their onset date based on the last dose of administration in either the feeder studies or the LTE, whichever is later, as follows:

In general:

- AEs occurring during treatment:  
An AE during treatment is defined as an AE with a date of onset  $\geq$  day of first dose of investigational product and  $\leq$  date of last dose of investigational product + 28 days.
- AEs occurring during follow-up:  
An AE during follow-up is defined as an AE with a date of onset  $>$  date of last dose of investigational product + 28 days and  $\leq$  date of last dose of investigational product + 84 days.
- AEs occurring during treatment and follow-up:  
An AE during treatment and follow-up is defined as an AE with a date of onset  $\geq$  day of first dose of investigational product and  $\leq$  date of last dose of investigational product + 84 days

The following are exceptions:

- For subjects in the “Randomised Placebo” treatment group with a switch to anifrolumab 300 mg in the LTE study, AEs with a date of onset  $\geq$  day of first dose of investigational product in the LTE study will not be considered in the categories above, except for those with an onset on the day of first dose of investigational product in the LTE that are recorded in the Phase 3 feeder studies.
- For subjects in the “All Anifrolumab” treatment group who were randomised to placebo in the Phase 3 feeder studies, AEs with a date of onset  $<$  day of first dose of investigational product in the LTE study and those with an onset on the day of first dose of investigational product in the LTE that are recorded in the Phase 3 feeder studies will not be considered in the categories above.

In general, an AE during LTE is defined as an AE in the categories above with a date of onset  $\geq$  day of first dose of investigational product in the LTE study. AEs with onset on the day of first dose of investigational product in the LTE, but which were recorded in the Phase 3 feeder studies will not be considered as occurring during the LTE.

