#### **4.1.3 Presentation of results**

All analyses will use SAS® version 9.3 or higher.

If not stated otherwise, summary tables will be presented according to the data used:

- Tables using combined data from feeder studies (i.e., studies D3461C00004 and D3461C00005) and LTE study will be presented by combined treatment group as defined in Section 2.1.6 (randomised anifrolumab 300 mg, randomised placebo, placebo feeder + placebo LTE, and all anifrolumab). For some tables, if mentioned explicitly, the additional supportive treatment groups placebo feeder + anifrolumab

300 mg LTE, and anifrolumab 150 mg feeder + anifrolumab 300 mg LTE will also be presented.

- Tables using data of the LTE study only will be presented by LTE treatment group as defined in Section 2.1.6 (randomised anifrolumab 300 mg, placebo feeder + placebo LTE, placebo feeder + anifrolumab 300 mg LTE, and anifrolumab 150 mg feeder + anifrolumab 300 mg LTE,)

For by-visit presentations, only baseline, Week 24, and Week 52 will be presented for the Phase 3 feeder studies. If not stated otherwise, results of a specific treatment group and visit will be suppressed if the summary is based on data of less than 25 subjects. For all other presentations, all available data for each analysis set will be used in the analyses. Data collected during the LTE study (including derived variables and baseline from the Phase 3 feeder studies) will be presented in listings sorted by LTE treatment group and subject number. A separate document will be produced containing the template table, listing, and figure shells.

Unless otherwise noted, categorical data will be presented using counts and percentages with the denominator for percentages being the number of subjects in the analysis set by treatment group. Percentages will be rounded to 1 decimal place; except 100% which will be displayed without any decimal places. Percentages will not be displayed for zero counts.

Unless otherwise noted, continuous variables will be summarised using the number of observations (n), mean, standard deviation (SD), median, minimum, and maximum. The minimum and maximum values will be displayed to the same level of precision as the raw data; the mean, median, and quartiles to a further decimal place; and the SD to 2 additional decimal places. CV% [REDACTED] will be presented with 1 decimal place.

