The event rate per 100 subject years including 95% CIs will be summarised for the following categories. Summaries of AESIs will be presented by AESI category (non-opportunistic serious infections, opportunistic infections, anaphylaxis, malignancy, herpes zoster, tuberculosis, influenza, vasculitis [non SLE], and major acute cardiovascular events) and preferred term. Summaries for SAEs will be presented by MedDRA system organ class and preferred term.

- Any AESI
- Any AESI by time interval for the first onset of event – alternative event rates
- Any AE leading to discontinuation of IP by time interval for the first onset of event – alternative event rates (combined feeder & LTE study, by preferred term)
- Any AESI – alternative event rates
- Any SAE (including events with outcome = death) (during treatment and during follow-up separately. No event rate for during follow-up will be presented)
- Any SAE (including events with outcome = death) by time interval for the first onset of event – alternative event rates

The event rate per 100 subject years will be summarised by MedDRA system organ class and preferred term for the following AE categories.

- Any AE (during treatment and during follow-up separately. No event rate for during follow-up will be presented)
- Any AE by descending preferred term (during treatment, and during the LTE treatment)
- Any AE with outcome = death
- Any SAE by descending preferred term (including events with outcome = death) (during treatment, and during the LTE treatment)
- Any AE leading to discontinuation of investigational product
- Any AE by relationship to investigational product (yes, no) (multiple occurrences of an AE in 1 subjects will only be counted once as related if at least one AE is related and as not related if all occurrences are not related)
- Any AE by maximum intensity (mild, moderate, severe) (i.e., multiple occurrences of an AE in 1 subjects will only be counted once with the maximum intensity in this AE)
- Any other significant AE

The alternative event rate per 100 subject years will be summarised by MedDRA preferred term for the following AE categories.

- Any COVID-19 related AE (for the LTE Study only, only subjects remaining in the study on 11-Mar-2020 will be included)
- Any SAE prior to the COVID-19 pandemic (for the LTE Study only)
- Any SAE during the COVID-19 pandemic (for the LTE Study only, only subjects remaining in the study on 11-Mar-2020 will be included)

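### In the separate follow-up SAE and AE displays, the default Randomised Placebo percentage counts subjects who switched to anifrolumab (about 31.5% on the plan's inputs) and cannot have a countable follow-up event

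*SAP*

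**What the plan says.** SAP 4.2.1.1 lists summaries of any SAE and of any AE to be shown "during treatment and during follow-up separately. No event rate for during follow-up will be presented". SAP 4.1.3 sets the default for categorical data, unless otherwise noted: counts and percentages, with the "denominator for percentages being the number of subjects in the analysis set by treatment group". The same section gives the columns for combined feeder and LTE data: "randomised anifrolumab 300 mg, randomised placebo, placebo feeder + placebo LTE, and all anifrolumab". It leaves table shells to a separate document.

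Four other provisions bear on the Randomised Placebo column.

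- SAP 2.1.6 defines the group as all subjects randomised to placebo in the feeder studies, "using data from start of feeder study up until switch to anifrolumab 300 mg or to end of LTE for subjects re-randomised to placebo". Switchers are therefore members.
- SAP 3: "The date of last dose of investigational product refers to the last dose during the LTE study for subjects who started the LTE study".
- SAP 3.1.1 classifies adverse events by onset, "based on the last dose of administration in either the feeder studies or the LTE, whichever is later". Follow-up runs from more than 28 to 84 days after that dose.
- SAP 3.1.1 also says that, for switchers within Randomised Placebo, events from the first dose "in the LTE study will not be considered in the categories above, except for those with an onset" on that first dosing day that were recorded in the feeder study.

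SAP 4.2.1 names Randomised Anifrolumab 300 mg against Randomised Placebo as the primary assessment.

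**The concern.** A switcher's follow-up window lies wholly after the switch, and every event after the switch is removed from this group. No event can satisfy both rules. The one exception, a feeder-recorded event on the first LTE dosing day, falls before the window opens. An event in a gap between the feeder study and the LTE also precedes the last LTE dose, so it counts as during treatment. Switchers are zeros by definition.

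The person-time rates deal with switching because exposure in this group stops the day before the first LTE dose. The follow-up displays have no rate, and nothing in SAP 4.2.1.1 replaces that protection with an at-risk denominator. These displays isolate events after dosing has stopped. A low placebo percentage that arises from the denominator could be read as an excess of events after stopping anifrolumab. For SAEs there is also an LTE-only follow-up table by LTE treatment group. For all AEs none is specified.

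**Working it through.** **Inputs.** Annual dropout is 30% on placebo and 20% on 300 mg, and 90% of completers enter the LTE (SAP 1.3, Protocol 8.2). Feeder placebo subjects are re-randomised 1:1 (SAP 1.2).

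**Reproducing the plan's follow-up times.** Assume dropouts leave at mid-year on average. Subject-years per feeder subject are then:

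- 300 mg: 0.9 + 0.8 x 0.9 x (0.9 + 0.72 + 0.576) = 2.481
- Placebo: 0.85 + 0.7 x 0.9 x 0.5 x (0.85 + 0.595 + 0.4165) = 1.436

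The documents give no feeder arm sizes. Back-solving gives 893/2.481 = 360 and 517/1.436 = 360. With 360 per arm the results are 893.2 and 517.1 subject-years, against 893 and 517 stated. The flow used below is therefore the one behind the plan's own figure.

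**Switcher share.** 0.70 x 0.90 x 0.50 = 0.315, or 113 of 360. Subjects who can be counted: 1 - 0.315 = 0.685. So 5.0% among non-switchers is displayed as 5.0% x 0.685 = 3.4%. As a cross-check, about 575 LTE subjects at 4:1 gives about 115 on placebo, hence about 115 switchers, and 115/360 = 31.9%.

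**Range.** With placebo dropout of 20% to 40% and LTE entry of 80% to 100%, the share runs from 0.6 x 0.8 x 0.5 = 0.24 to 0.8 x 1.0 x 0.5 = 0.40. The factor then runs from 0.76 to 0.60.

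**What the pair would show with no drug effect.** Call dropouts and completers who do not enter the LTE leavers.

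- Per 100 in Randomised Placebo: 30 + 7 = 37 leavers, 31.5 staying on placebo, 31.5 switchers.
- Per 100 on 300 mg: 20 + 8 = 28 leavers, 72 entrants.

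The documents give neither leaver risk nor follow-up capture, so the rows below are assumptions. Values are relative to an LTE entrant's risk.

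| Assumption | 300 mg | Randomised Placebo | Ratio |
|---|---|---|---|
| Equal risk, all observed | 1.00 | 68.5/100 = 0.685 | 1.46 |
| Leavers at twice the risk | (56 + 72)/100 = 1.28 | (74 + 31.5)/100 = 1.055 | 1.21 |
| Leavers at half the risk | (14 + 72)/100 = 0.86 | (18.5 + 31.5)/100 = 0.50 | 1.72 |
| Equal risk, half of dropouts observed | (10 + 8 + 72 x 0.756)/100 = 0.724 | (15 + 7 + 31.5 x 0.6715)/100 = 0.432 | 1.68 |

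In the last row, 0.756 = 0.512 + 0.244 and 0.6715 = 0.343 + 0.3285: three-year LTE completers plus half of LTE dropouts.

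**Removing switchers only.** Leavers become 37/68.5 = 54% of the remaining placebo subjects, against 28% on 300 mg. With all subjects observed, the ratio is 1.28/(105.5/68.5) = 0.83 with leavers at twice the risk and 0.86/(50/68.5) = 1.18 at half. Placebo Feeder + Placebo LTE has 18.5 leavers in 50 (37%). Its ratios are 1.28/(68.5/50) = 0.93 and 0.86/(40.75/50) = 1.06. At equal risk with half of dropouts observed, that column still reads 0.724/((11 + 21.15)/50) = 1.13 over all subjects, and 1.00 with an at-risk denominator.

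**The case against.** The strongest reply is that SAP 4.2.1.1 never names this percentage. It says only that no rate is shown, and elsewhere in the section it asks for number and percentage explicitly. The default yields to anything otherwise noted, and the shells are not available here. A count-only shell or a footnote would remove the problem. This stands as a condition on the finding, but as written the SAP text points to the full-group denominator.

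Little also depends on these tables. No formal comparison is planned, and AESI and SAE rates combine treatment and follow-up on person-time. Disposition by feeder study shows LTE treatment, so a reader could find the number of switchers and rescale. The direction is to lower the placebo figure, so the denominator effect would not hide harm from anifrolumab. All of this stands and keeps the point minor.

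A reader might infer that the displayed placebo percentage is two-thirds of the true at-risk value, or that the displayed ratio will be 1.46. The documents support neither. The 0.685 is relative to all non-switchers, whether or not they reach follow-up. With half of dropouts observed, the placebo figure is 0.432 of the at-risk value, and the 300 mg figure also falls, to 0.724.

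**Conclusion.** The point holds as a minor one. If default percentages are printed, about 31.5% of the Randomised Placebo denominator (24% to 40% over the range above) cannot contribute an event. The displayed percentage is then about 0.685 of that among non-switchers, with no matching effect on 300 mg. The mechanism rests on the SAP text alone. Its size rests on planning values, and the realised number of switchers will set the actual factor. The size of the displayed between-group ratio is not determined by the documents.

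Two stronger conclusions are tempting. One is that the primary safety comparison is biased. It is not: those rates use person-time that ends at the switch, and the LTE-only SAE follow-up table is also unaffected. The other is that Placebo Feeder + Placebo LTE should replace Randomised Placebo for follow-up. SAP 2.1.6 labels Randomised Placebo primary and the other group supportive, and the denominator can be corrected without changing the comparator.

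**What to change.** In SAP 4.2.1.1, add to both the SAE and the AE follow-up items:

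> Percentages during follow-up are based on subjects in study beyond last dose + 28 days on the treatment shown, and this N is displayed; subjects who switched to anifrolumab are not counted in the Randomised Placebo follow-up denominator.

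Add a footnote with two statements.

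1. The Week 52 limit in SAP 2.1.6 does not apply to these displays, because SAP 3.1 confines the related Day 378 restriction to visit-based analyses. This is needed because SAP 2.1.6 says that non-entrants "but that would have been re-randomised to placebo are included in this treatment group up to Week 52". The last feeder dose is at Week 48, so the follow-up window of completers who do not enter the LTE opens at Week 52, and a literal cut would remove it.
2. Placebo Feeder + Placebo LTE, already in the same table, is closer in case mix to 300 mg: 37% leavers against 28%, compared with 54% in Randomised Placebo without switchers.

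Keep Randomised Placebo as the pre-specified primary placebo group.

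The cost is this wording and one derived flag for entry into follow-up, with no new data. The downside is that the denominator is conditional on reaching follow-up, a post-randomisation event, and some case-mix difference remains. The percentages should be read as descriptive only.

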## **2. ANALYSIS SETS**

### **2.1 Definition of analysis sets**

#### **2.1.1 Full analysis set**

All subjects enrolled in Studies D3461C00004 or D3461C00005 will be included in the main analysis of the LTE study, even if they do not enter the LTE study. Therefore, the full analysis set will consist of all subjects who were randomised and received at least 1 dose of investigational product in the Phase 3 feeder Studies D3461C00004 or D3461C00005. Subjects will be analysed according to the Intention-To-Treat principle (ie, as randomised). Subjects who withdraw consent to participate in the study will be included up to the date of their study termination.

Any major deviations from randomised treatment in the Phase 3 feeder studies or the LTE study will be listed and considered when interpreting the safety data.

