For time to event analyses and calculation of alternative event rates only, the following rules will be applied for imputing (partially) missing onset dates prior to analysis: If an AE has a (partially) missing onset date, it will be imputed with the earliest possible date on or after the day of first administration of investigational product given the available start and stop date information. If the available start or stop date information indicate that the AE started prior to first administration of investigational product, no imputation of the start date will be done.

For the by timepoint analysis of anaphylaxis, hypersensitivity, and infusion related reactions, an AE at a visit is defined as an AE with a date of onset  $\geq$  day of administration of investigational product at the respective visit and  $\leq$  date of administration of investigational product at the following visit (or  $\leq$  date of last dose of investigational product + 84 days for the last visit with investigational product). Analogous to assignment of AEs to time intervals, AEs with (partially) missing date will be assigned to the earliest possible visit giving the available start and stop date information, in the study (feeder phase 3 or LTE) they were recorded in.

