#### **4.1.2 Visit windows**

For visit-based analyses, the variables will be summarised based on the scheduled days with adjusted analysis-defined visit windows. If not stated otherwise, for the Phase 3 feeder studies, only Baseline, Week 24, and Week 52 will be presented in visit-based summaries. The adjusted analysis-defined windows are summarised below:

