### **4.2.1 Analysis of the primary variables (safety variables)**

If not stated otherwise, safety variables will be summarised by combined treatment group for the full analysis set.

The primary assessment will be the comparison between the treatment groups “Randomised Anifrolumab 300 mg” and “Randomised Placebo”. The “All Anifrolumab” treatment group will be used to assess rare events.

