Cardiovascular outcome events as determined by the CV-EAC will be presented separately, summarising the number of AEs submitted for adjudication and the outcomes of the adjudication including MACE classification. Site reported cardiovascular AEs, cardiovascular SAEs, and their corresponding adjudicated outcomes will be listed.

The time to first onset of an AE in an AESI category will be presented separately for each AESI category as a Kaplan-Meier plot annotated with the number of subjects at risk every 6 months.

Furthermore, the alternative event rates per 100 subject years for the first onset of herpes zoster will be summarized for events overall and by time intervals). The following subcategories will also be considered in this summary: SAE (including events with outcome of death), AE leading to discontinuation, and AE by maximum intensity (mild, moderate, and severe). This summary will also be presented for the additional supportive treatment groups placebo feeder + anifrolumab 300 mg LTE, and anifrolumab 150 mg feeder + anifrolumab 300 mg LTE.

Furthermore, AESIs (by event type and preferred term), SAEs (during treatment and during follow-up separately, by system organ class and preferred term) during LTE will be summarised by LTE treatment group. Summaries of deaths, AESIs by time interval and SAEs by time interval will also be presented for the additional supportive treatment groups placebo feeder + anifrolumab 300 mg LTE, and anifrolumab 150 mg feeder + anifrolumab 300 mg LTE.

The event rate per 100 subject years and number and percentage of subjects with at least one anaphylaxis, hypersensitivity, and infusion-related reaction (investigator), respectively, will be summarised overall as well as for the following respective subcategories: SAE (including events with outcome of death), AE leading to discontinuation, and AE by maximum intensity (mild, moderate, and severe). Furthermore, these AE categories will be presented graphically over time as percentage of subjects with a respective AE at a respective visit according to the definition as given in Section 3.1.1. These summaries will also be presented for the additional supportive treatment groups placebo feeder + anifrolumab 300 mg LTE, and anifrolumab 150 mg feeder + anifrolumab 300 mg LTE.

Infections, opportunistic infections, and non-opportunistic infections will be summarised with the same subcategories as given above. This summary will also be presented for the additional

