#### **4.2.1.6 Laboratory variables**

Observed values and changes from baseline of laboratory data for haematology, clinical chemistry, and fasting lipid profile will be summarised by visit. The summary statistics presented will be minimum, 1st quartile, median, 3rd quartile, maximum, mean, and SD.

Shift plots (scatter plots) presenting baseline values versus minimum post-baseline values (neutrophils, lymphocytes, monocytes, and haemoglobin only) and maximum post-baseline values (creatinine, creatinine kinase, blood urea nitrogen, alanine aminotransferase, aspartate aminotransferase, bilirubin), respectively, will be provided. A diagonal reference line indicating no change and horizontal and vertical reference lines indicating the limits of the reference ranges will also be displayed on the shift plots.

If any laboratory variables show any unusual features (high or low values or a general shift in the data points) at specific visits, then shift plots of these data may also be produced. This will be discussed and agreed upon during the BDR meeting.

[figure not shown]
For each laboratory parameter with available criteria, the number and percentage of subjects with TELVC values will be summarised by visit. Additionally, the number and percentage of subjects with at least 1 TELVC value will be presented. Percentages will be based on subjects with a measurement at baseline and at least 1 subsequent measurement of the variable (at the respective visit).

[figure not shown]
The number and percentage of subjects with laboratory values below, within, or above the corresponding reference ranges [REDACTED] will be presented as shift tables from baseline to maximum and minimum on-treatment value, respectively.

[figure not shown]
Urinalysis will be summarised as shift tables from baseline to the last on-treatment value for each parameter. Furthermore, the number and percentage of subjects with treatment-emergent changes will be summarised by parameter. Percentages for the summary of treatment-emergent changes will be based on subjects with a measurement at baseline and at least 1 subsequent measurement of the variable.

[figure not shown]
In order to identify potential Hy's Law cases, a shift table of maximum on-treatment total bilirubin against maximum on-treatment ALT, and maximum on-treatment AST expressed as multiples of ULN will be presented.

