#### **4.2.3.3 Exposure**

All summaries of exposure will be presented by combined treatment group as well as by LTE treatment group for the full analysis set.

Summary statistics will be provided for the duration of exposure. Descriptive statistics including quartiles will be provided in addition to the number and percentage of subjects treated  $\geq 24$  weeks,  $\geq 52$  weeks (both for combined data from feeder and LTE study only),  $\geq 76$  weeks,  $\geq 104$  weeks,  $\geq 128$  weeks,  $\geq 156$  weeks,  $\geq 180$  weeks, and  $\geq 208$  weeks. Furthermore, the total treatment days and total subject-years of exposure will be presented.

The number and percentage of subjects with infusions (for combined data from feeder and LTE study) and infusions during LTE (for LTE study), respectively, will be presented by total number of infusion (i.e., 1, 2, 3, etc). For weeks 24 (for combined data from feeder and LTE study only) and all scheduled visits in the LTE study (including week 52/LTE Day 1), the number and percentage of subjects with infusion/ no infusion will also be presented.

Furthermore, the time to discontinuation of investigational product will be presented as Kaplan-Meier plot including the number of subjects at risk (ie, still on investigational product) at weeks 24, 52, 76, 104, 128, 156, 180, and 208. Subjects in the “Randomised Placebo” treatment group who switched to anifrolumab will be censored using the last infusion of placebo as the censoring date and in the All Anifrolumab treatment group (using the first infusion in the LTE as day of first infusion). In interim analyses subjects who did not discontinue IP or completed/withdrew from study will be censored using the last infusion as the censoring date.

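### The by-visit plots of infusion-linked reactions have no stated denominator; under the SAP default, an equal risk would look about 2.3 to 3.4 times higher for Randomised Anifrolumab 300 mg than for Randomised Placebo in the LTE

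*SAP*

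**What the plan says.** SAP 4.2.1.1 first gives overall event rates and percentages for the three reaction types, and then adds that "these AE categories will be presented graphically over time as percentage of subjects with a respective AE at a respective visit". It refers to SAP 3.1.1 for the definition. There, "an AE at a visit is defined as an AE with a date of onset" from the infusion date at that visit up to and including the infusion date at the next visit. This fixes the numerator only.

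The denominator has to come from the general rules. For categorical data, SAP 4.1.3 sets the "denominator for percentages being the number of subjects in the analysis set by treatment group" where nothing else is noted. SAP 4.2.1 adds that, by default, "safety variables will be summarised by combined treatment group for the full analysis set". Under SAP 2.1.1, "the full analysis set will consist of all subjects who were randomised and received at least 1 dose of investigational product" in a feeder study, whether or not they entered the LTE. In SAP 2.1.6, placebo subjects who switch to anifrolumab belong to Randomised Placebo, with data used only until the switch.

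Elsewhere the SAP replaces the default explicitly. Vital-sign changes (4.2.1.2), laboratory changes by visit (4.2.1.6) and disease-related treatments by visit (4.2.3.2) each have their own denominator. The reaction plots do not.

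For the feeder year, SAP 4.1.2 states that by default "only Baseline, Week 24, and Week 52 will be presented in visit-based summaries"; 4.1.3 repeats the limit.

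**The concern.** A reaction of this kind can be counted at a visit only if the subject was infused at that visit. If the whole group is the denominator, the curve mixes the risk per infusion with the share of the group still being infused. That share differs sharply between the two primary groups, because half of the placebo subjects who enter the LTE leave Randomised Placebo on LTE Day 1. The placebo curve would drop at that point and keep falling faster than the anifrolumab curve even with no drug effect. SAP 4.2.1 names this pair as the primary assessment.

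Two further features affect the same plot. The feeder-year limit would leave out most feeder infusions. The closed visit interval also counts a reaction on an infusion day at two visits: the one where it occurred and the one before.

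**Working it through.** **Inputs.** SAP 1.3: annual dropout 20% (300 mg) and 30% (placebo, 150 mg); 90% of feeder completers enter the LTE; follow-up of 893, 517 and 1343 subject-years. SAP 1.2: 1:1 re-randomisation of placebo subjects; LTE infusions from Week 0 to Week 152. The documents give no feeder arm sizes.

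**Reproducing the plan's follow-up.** Take dropout as linear within each year, so a year with dropout d contributes 1 − d/2 per subject at its start.

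- 300 mg: 0.9 + 0.8 × 0.9 × (0.9 + 0.72 + 0.576) = 2.481 years per subject; 893 / 2.481 = 359.9.
- Randomised Placebo: 0.85 + 0.7 × 0.9 × 0.5 × 0.85 × (1 + 0.7 + 0.49) = 1.436; 517 / 1.436 = 359.9.
- All Anifrolumab, with 20% dropout in the LTE for those moved to 300 mg: the 150 mg arm back-solves to 89.9.

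Arms of 360, 360 and 90 return 893.2, 517.1 and 1343.2. The sizes are back-solved, so this shows consistency and is not an independent proof. The same model gives 0.9 × (0.8 × 360 + 0.7 × 360 + 0.7 × 90) = 543 LTE entrants against the stated 575 or so. Arm sizes cancel in the ratios below.

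**Share of each group infused.** After y whole LTE years and a fraction f of the next, retention is R = (1 − d)^y × (1 − d × f). The share is 0.8 × 0.9 × R for 300 mg and 0.7 × 0.9 × 0.5 × R for Randomised Placebo. Placebo Feeder + Placebo LTE contains about half of the feeder placebo subjects, by re-randomisation or by the separate assignment of non-entrants, so its share is 0.7 × 0.9 × R.

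| LTE week | 300 mg | Randomised Placebo | Ratio | Ratio v Placebo Feeder + Placebo LTE |
|---|---|---|---|---|
| 0 | 72.0% | 31.5% | 2.29 | 1.14 |
| 52 | 57.6% | 22.05% | 2.61 | 1.31 |
| 104 | 46.1% | 15.4% | 2.99 | 1.49 |
| 152 | 37.6% | 11.2% | 3.37 | 1.68 |

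With exponential dropout the Week 152 ratio is 3.38.

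**Illustration.** Assume a 1% risk per infusion in both groups, each reaction counted once. The plot shows 0.72% v 0.32% at LTE Week 0 and 0.38% v 0.11% at Week 152. With subjects infused at the visit as denominator, both groups show 1% at every visit.

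**Sensitivity.** With equal dropout the ratio is 2.0 throughout, from re-randomisation alone. With 20% v 25% it runs from about 2.1 to 2.6.

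**Closed interval.** If all reactions fall on the infusion day, the 300 mg point at LTE Week 0 also takes in those of Week 4: 0.72% + 0.72% × (1 − 0.2 × 4/52) = 1.43%. For Randomised Placebo it is 0.315% + 0.315% × (1 − 0.3 × 4/52) = 0.62%. The levels about double; the ratio stays at 2.3.

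**Feeder visits.** Infusions every 4 weeks from Week 0 to Week 48 make 13. If only Baseline and Week 24 are shown, the closed interval brings in infusion-day reactions from Weeks 0, 4, 24 and 28. Those of Weeks 8 to 20 (4) and 32 to 48 (5) are absent: 9 of 13.

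**The case against.** The strongest reply is that the denominator is inferred. SAP 4.2.1.1 does not name one, SAP 3.1.1 ties the event to an infusion at the visit, and SAP 4.1.3 suppresses by-visit results based on fewer than 25 subjects, which suggests visit-specific numbers. The figure shells are a separate document and may settle it. This stands in part: a reader might infer that the plots are certain to use the whole group, and the documents do not prove that. But the suppression rule sets no denominator, and with back-solved arms of 360 about 40 placebo subjects are still infused at Week 152 (360 × 11.2%), so it would not hide these points. The only denominator the SAP does state is the whole group.

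The second reply is that little depends on this plot, and it largely stands. No formal comparison is planned. The overall rates per 100 subject-years for the same reactions end a switcher's placebo exposure the day before the first LTE infusion (SAP 3.1.1). Anaphylaxis, as an AESI category, also has rates by time interval and a Kaplan-Meier plot. Late counts are small: at an assumed 1% risk, about 40 placebo subjects give 0.4 expected events at Week 152. The plot nevertheless remains the SAP's visit-level display for hypersensitivity and infusion-related reactions, which are not in its list of AESI categories.

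Three further inferences go too far. The 2.3 to 3.4 range does not hold for every placebo comparison. The whole-group denominator need not understate the risk per infusion, since double counting can lift the plotted value to about 1.4% when the true risk is 1%. Nor are 11 of the 13 feeder infusions lost under the present interval; for infusion-day reactions it is 9.

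**Conclusion.** The concern holds as a gap that the SAP's own default fills badly. Read as written, the plan keeps in the denominator subjects who cannot have an event at the visit. For Randomised Anifrolumab 300 mg against Randomised Placebo, an equal risk per infusion would appear about 2.3 times higher at LTE Week 0 and about 3.4 times at Week 152. These factors rest on the planning assumptions for dropout and LTE entry; the part due to 1:1 re-randomisation alone is 2.0. Against Placebo Feeder + Placebo LTE the factor is about 1.1 to 1.7.

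Whether the feeder-year limit governs this plot is open, since it yields to any contrary statement and the plot has its own infusion-based definition; nothing says that it does not. The double counting follows directly from SAP 3.1.1.

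This should be corrected, but the primary safety rates do not depend on it.

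**What to change.** - **SAP 4.2.1.1:** state that in the by-visit presentation of these three reactions the denominator at each visit is the number of subjects in the group who received an infusion at that visit. Print that number under the plot.
- **SAP 4.2.1.1:** state that all feeder infusion visits are shown, as an exception to the by-visit limit in 4.1.2 and 4.1.3.
- **SAP 3.1.1:** end the visit interval before the next infusion date (< in place of ≤), so that a reaction on an infusion day counts once. This makes the second change more necessary: with only Baseline and Week 24 shown, infusion-day reactions from 13 − 2 = 11 feeder infusions would then be absent.
- **Figure shells:** check that they agree.

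The cost is a few sentences and some programming, with no new data. SAP 4.2.3.3 plans that "the number and percentage of subjects with infusion/ no infusion will also be presented" only for Week 24 and the LTE visits, so counts for the other feeder visits must be derived from existing dosing records. Late placebo points will rest on small numbers, which the reader will be able to see.
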